### 11.9.2 Mechanistic Laboratory Data Recording/Reporting

Outputs of the mechanistic studies will be recorded as follows:

- 1. Initial observations recorded in paper based laboratory notebooks according to standard practice.
- 2. Digital images associated with experimental outputs to be held locally on portable, encrypted solid-state hard drives.
- Digital images and experimental outputs uploaded on to a secure web page shared between the four mechanistic labs. Times of data uploads will be logged.
- 4. Following data analysis and summarisation, all data will be reported firstly to the DMEC and via that committee to the TSC and TMG. Reports will be drafted for internal discussion followed by approved submission of the outputs to peer reviewed journals.

## 11.10 Data Handling & Record Keeping

## 11.10.1 Confidentiality

The Chief Investigator is the 'Custodian' of the data and will ensure that information with regards to study participants will be kept confidential managed in accordance with the Data Protection Act 1998, NHS Caldicott Guardian 2010, The Research Governance Framework for Health and Social Care 2005 and Research Ethics Committee Approval.

Personal data and any sensitive information required for the HABSelect Trial will be collected directly from trial participants and hospital notes. Identifiable information to be collected from the participants include, full name, DOB, NHS number for female and contact details after couples consent to the trial. Male NHS number will be collected only if consent for donation of residual sperm sample in HBRC has been given. This information will be entered to Identification Log, which also includes couple study ID and used to contact participants but will not leave the study site. All case report forms (CRFs) will be pseudonymised. All staff involved in the HABSelect share the same duty of care to prevent unauthorised disclosure of personal information.

The trial data will be made available to suitably qualified members of the research team, sponsor representatives, study monitors and auditors, the REC and regulatory authorities as far as required by law.

No data that could be used to identify an individual will be published. The participants will be anonymised with regards to any future publications relating to this study.

## 11.10.2 Study Documents

The following documents will be used in the HABSelect trial:

- A signed protocol and any subsequent amendments
- PCTU monitoring assessment template for the trial team to follow as detailed by the Monitoring section
- Current/Superseded Couple Information Sheets
- Current/Superseded Consent Forms (as applicable)
- Human Biomaterials Resource Centre, University of Birmingham Donation of Human Tissue PIS and associated consent form
- GP Letter to inform them of participants inclusion in the HABSelect Trial
- Invitation Letter for potential participants to invite them to the study
- Indemnity documentation from sponsor
- Conditions of Sponsorship from sponsor
- Final R&D Approval
- Signed site agreements and laboratory contracts
- Ethics submissions/approvals/correspondence
- CVs of CI and site staff
- Laboratory accreditation letter, certification and normal ranges for all laboratories to be utilised in the study
- Site Research Staff Delegation log
- Certificates of the training in the study intervention for the site Embryologist(s)/Andrologists(s)
- Participant identification log
- Screening log
- Enrolment log
- Site visit log
- Protocol training log
- Correspondence relating to the trial
- Communication Plan between the CI/PI and members of the study team
- Case Report Forms (CRFs)
- Provisional or conditional R&D letter
- GCP/RGF certificates of the patient-contacting study team member(s)

- Trial specific SOPs
- Adverse Events log

#### 11.10.3 Case Report Forms

For all participating couples, pre-interventional trial data will be recorded in the patient notes which will be completed by the ACU/Fertility clinic team (i.e. clinicians, embryologists). The following data will be abstracted from the notes and recorded on CRF for the trial by the research nurse or another appropriately trained staff blinded to the participant allocation, relying on the research support in each of the recruiting hospitals. Any available missing information will be obtained from trial participant prior to discharge from the Fertility Centre to the community ante-natal care.

#### **Pre-Intervention Phase**

- Eligibility criteria for both partners
- Demographic assessments for both partners
- Previous fertility treatment for both partners
- Gynaecological and obstetric history for female
- Hormonal profile for female partner
- Semen profile for male partner

#### Intervention Phase

- Four equal aliquots obtained from the remainder of the semen sample
- Initial Sperm concentration
- HBS score
- Number of pronucleate zygotes formed
- Number of embryos transferred
- Biochemical pregnancy indicators
- Clinical pregnancy indictors (as confirmed by USG scan)

Post Intervention Phase:

- Successful live birth ≥37 completed weeks since embryo transfer or last menstrual period.
- Clinical pregnancy rate based on detection of fetal heartbeat or presence of fetal sac at 6-9 weeks' gestation
- Miscarriage rates defined as pregnancy loss at any time post confirmation of

clinical pregnancy

- Live births at < 37weeks' gestation.
- Serious adverse events

All of the above will be based on data gathered from the ICSI cycle with first fresh embryo transfer per couple.

Extra

- Additional Information/Note to File CRF
- Final Study Status /Early Withdrawal CRF

CRFs will be pseudonymised using couple unique ID allocated during enrolment. This code will consist of the trial site code followed by consecutive numbers starting at 001. Site codes are documented in Appendix 2.

E.g.: Birmingham Women Fertility Centre (0119), couple number 1 (001): 0119/001

## 11.10.4 Data collection, processing and monitoring

The PCTU will activate and deploy a web-based trial database. PCTU trial coordinator, monitor, quality assurance manager, data manager, statistician, study CI and Clinical Advisors will have full access to the entire database for monitoring, coordinating, safety reporting and analysis purposes. A set of trial specific CRFs will be created. Participating sites will record the required data item via the internet using secure socket layer encryption technology. Missing and discrepant data will be flagged by the trial coordinator, trial monitor or trial statistician by following data cleaning and quality control procedures with additional data validations raised during monitoring visits. Schedule of Assessment table in first part of Section 11 provides a summary of assessment procedures that will be undertaken during the HABSelect study.

#### 11.10.5 Format

Relevant trial data will be transcribed from participants' notes into CRF. Source data will comprise of the research clinic notes, hospital notes, hand-held pregnancy notes and laboratory results.

Women will be encouraged to report pregnancies, miscarriages and deliveries occurring between clinic visits or presenting at non-participating hospitals to the research nurse or assistant. Self- reports will be verified against clinical notes.

#### 11.10.6 Data Completeness

Compliance with the clinical procedure will be checked at the end of each week by the trial coordinator who will ensure that the participating sites' Day 0 and Day of embryo transfer entries have been uploaded onto the online database as required. The research nurse or assistant will also record the use of the Hydak slides and PICSI plates allowing the Trial Coordinator to check regularly against the delivered inventory of each trial participant. In an effort to improve compliance, sites failing to upload their data or report inventory use will be contacted by telephone or email. Any protocol deviations will be recorded and notified to DMC and any serious breaches of the protocol or GCP will be reported to the Sponsor in line with Sponsor SOP.

## 12. SAFETY

### 12.1 Adverse Events (AE)

The IVF intervention under evaluation is limited to the process of fertilising the eggs (Day 0), using a CE marked device in both arms of the trial. There is no on-going intervention or routine follow up planned until the final outcome measure; as a consequence the clinical advisors and sponsor have determined that no additional 'active' monitoring for patient safety and adverse event reporting is required.

Outcomes related to pregnancy success (biochemical and clinical pregnancy) will be captured whilst the patient is still under the clinical supervision of the IVF clinic. If the pregnancy is confirmed the woman will then pass to standard ante-natal care based on her own risk criteria and pregnancy outcome will be reported to the IVF clinic using established local protocols for IVF clinical audit.

### 12.2 Serious Adverse Event (SAE)

An SAE fulfils at least one of the following criteria:

- Is fatal results in death (NOTE: death is an outcome, not an event)
- Is life-threatening
- Requires inpatient hospitalisation or prolongation of existing hospitalisation
- Results in persistent or significant disability/incapacity
- Is a congenital anomaly/birth defect
- Is otherwise considered medically significant by the Investigator

## 12.2.1 Expected SAEs

It is possible that during their pregnancy, participants will be admitted to hospital for treatment or monitoring of their pregnancy. Expected SAEs will include hospitalisations for the following events.

- routine treatment or monitoring of miscarriage or threatened preterm birth, not associated with any deterioration in condition including :
  - Premature Rupture Of Membranes or suspected PROM
- treatment, which was elective or pre-planned, for a pre-existing condition that is unrelated to the indication under study, and did not worsen including:

- Elective Caesarean Section,
- admission to a hospital or other institution for general care, not associated with any deterioration in condition including:
  - Hospitalisation for rest
  - Hospitalisation for observation or monitoring of pregnancy
  - Hospitalisation for Maternal Discomfort
  - Hyperemesis which is quickly resolved.

Treatment on an emergency, outpatient basis for an event not fulfilling any of the definitions of serious given above and not resulting in hospital admission will not be treated as an SAE.

Pregnancy related SAEs recorded in the medical notes will be captured by each site as part of the pregnancy outcome and recorded on an SAE log. All SAEs will be notified to the trial coordinator and chief investigator who will maintain a central log of all SAEs for onward reporting. These will be reported according to PCTU standard procedures.

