## 12.3 Notification and Reporting of Serious Adverse Events

The National Research Ethics Service defines related and unexpected SAEs as follows:

- related' resulted from administration of any research procedure.
- 'unexpected' this type of event is not listed in the protocol as an expected occurrence

Only Serious Adverse Event (SAEs) that are considered to be 'related' and 'unexpected' are to be reported to the sponsor and PCTU QA manager within 24 hours of learning of the event and to the Main REC within 15 days in line with the required timeframe.

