#### 15.4.2 Data Monitoring and Ethics Committee

The DMEC will adopt a DAMOCLES charter to define its terms of reference and operation in relation to oversight of the HABSelect trial. They will not be asked to perform any formal interim analyses of effectiveness. They will, however, have access to unblinded treatment allocations obtained from the independent statistician at the PCTU, and for their meetings they may wish to see copies of data accrued to date, or summaries of that data by treatment group. They will also consider emerging evidence from other trials or research on PICSI compared with PVP-ICSI. They may advise the chair of the Trial Steering Committee at any time if, in their view, the trial should be stopped for ethical reasons, including concerns about patient safety. DMEC meetings will be held every 6 months, the first after recruitment has commenced. Members of HABSelect DMEC are listed in Section 1.7.

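### Section 12.2.1 counts admission for elective caesarean as an SAE and leaves other birth admissions undefined, so crude SAE counts by arm are partly confounded with the primary outcome

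*Protocol*

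**What the plan says.** Protocol section 12.2 defines an SAE by the usual criteria, one of which is "Requires inpatient hospitalisation or prolongation of existing hospitalisation". It makes no exception for admission to give birth.

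Section 12.2.1 then says "Expected SAEs will include hospitalisations for the following events". Two items on the list matter here: "Elective Caesarean Section" and "routine treatment or monitoring of miscarriage or threatened preterm birth, not associated with any deterioration in condition". These are SAEs labelled as expected; they are not exclusions. The one exclusion in the section is for emergency outpatient treatment that does not lead to admission. Vaginal birth and emergency caesarean are neither listed nor excluded.

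On capture, section 12.2.1 says "Pregnancy related SAEs recorded in the medical notes will be captured by each site as part of the pregnancy outcome", followed by "All SAEs will be notified to the trial coordinator and chief investigator who will maintain a central log of all SAEs". Section 12.1 plans no active safety monitoring, and section 11.2 schedules no trial-specific follow-up after the IVF procedure.

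Section 12.3 restricts 24-hour reporting to SAEs that are both related and unexpected, where unexpected means "this type of event is not listed in the protocol as an expected occurrence". Under section 15.4.2 the DMEC may ask for "summaries of that data by treatment group" and may advise stopping over patient safety. Section 5.4.3 also promises an interim safety analysis.

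**The concern.** The primary outcome is live birth at 37 weeks or later. Under the rules as written, one way of delivering that outcome generates an SAE. Section 12.2.1 files elective caesarean under pre-planned treatment for a pre-existing condition unrelated to the indication. In this trial it is a route to the primary endpoint.

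Two problems follow.

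- **Efficacy enters the safety count.** A couple who do not conceive have almost no described way of contributing an SAE, whereas a couple who succeed may contribute one by succeeding. If the arms differ in live birth rate, the crude SAE counts will tend to differ even when the device does no harm.
- **Recording may differ between sites.** One site may read the hospitalisation criterion in 12.2 literally and log every birth. Another may log only the elective caesareans that 12.2.1 names. Later analysis cannot cleanly repair inconsistent logging, because the rule governs what is recorded.

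The DMEC may look at these counts by arm, and the final report is likely to show them.

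**Working it through.** **1. Reproducing the design figure.** Sections 13.4 and 13.5 give a 5-point improvement, 90% power and 3,266 couples. They name no control rate. Section 5.1 gives 24% per cycle as the average live birth rate. Assume two-sided alpha 0.05 and 24% v 29%.

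Unpooled formula: n = (1.960 + 1.282)² × (0.24×0.76 + 0.29×0.71) / 0.05² = 10.507 × 0.3883 / 0.0025 = 1,632.01. This rounds up to 1,633 per arm, or 3,266 in total, which is the stated figure. The pooled-variance formula gives 1,636 per arm, or 3,272. So 24% v 29% is a fair reading of the design, though still an inference.

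**2. Births per arm.** Section 13.4.1 expects 3,357 outcomes after 10% loss, about 1,678 per arm.

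- PVP-ICSI: 1,678 × 0.24 = 403
- PICSI: 1,678 × 0.29 = 487
- Difference: 84

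**3. Extra SAEs without harm.** Let s be the share of births logged as SAEs. The excess in the PICSI arm is 1,678 × 0.05 × s. The protocol gives no caesarean share, so 10–30% is an assumption.

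| Births logged (s) | PVP-ICSI | PICSI | Excess |
|---|---|---|---|
| 10% | 40 | 49 | 8 |
| 20% | 81 | 97 | 17 |
| 30% | 121 | 146 | 25 |
| 100% | 403 | 487 | 84 |

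The first three rows follow from what 12.2.1 names. The last row needs every birth admission to be read into 12.2. Per randomised woman the ratio for birth-related SAEs is 0.29/0.24 = 1.21 in every row; per birth it is 1.00.

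**4. Miscarriage admissions pull the other way.** They are on the same list. Section 13.4 assumes that miscarriage is inversely related to live birth, and section 5.4.3 expects PICSI to reduce early loss. Suppose the 5-point gain comes wholly from miscarriage falling from 10% to 5% of women (assumed), with a share m of miscarriages admitted. SAEs per woman are then 0.24s + 0.10m under PVP-ICSI and 0.29s + 0.05m under PICSI, a difference of 0.05(s − m). The sign depends on whether births are logged more often than miscarriages are admitted.

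- s = 15%, m = 50%: 0.086 v 0.0685, ratio 0.80
- s = 50%, m = 10%: 0.130 v 0.150, ratio 1.15
- s = 100%, m = 50%: 0.290 v 0.315, still 0.025 × 1,678 = 42 more under PICSI

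**5. A per-pregnancy denominator.** Table 2 in section 5.3.2 shows clinical pregnancy almost equal overall in the earlier US trial (47.8% v 47.3%), with miscarriage at 10.0% v 4.3%. If PICSI acts in that way, dividing by clinical pregnancies leaves the birth-related ratio at 1.21. That denominator alone would not remove the problem.

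**The case against.** Four objections carry weight.

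- **Only elective caesarean is named.** A reader might infer that the protocol logs every birth as an SAE. It does not say so; that reading comes from the general hospitalisation criterion in 12.2. The corresponding comparison (84 extra events, z = 3.28, p = 0.001) merely restates the assumed primary effect and is no independent evidence of a safety artefact. This stands, and 84 is an upper bound only.
- **Collection is not confined to pregnancies.** A reader might infer that SAEs in women who do not conceive are never collected. Section 12.2.1 requires all SAEs to be notified, section 11.10.3 lists SAEs as case report form data, and section 10.5.2 aims to follow women who discontinue for safety outcomes. The schedule in section 11 appears to mark adverse events only at end of pregnancy, but its columns are broken in the text at hand. This stands too: pregnancy outcome is the only route described, not the only one permitted.
- **An effective PICSI arm need not look more harmful.** Step 4 shows that miscarriage admissions can cancel or reverse the excess. A claim of bias against PICSI is not supported.
- **The consequence is indirect.** The protocol sets no SAE comparison between arms and no safety stopping rule. The DMEC could see births beside SAEs, and safety-table denominators are commonly left to the SAP, which is not shown. Nor does an unlisted mode of birth trigger expedited reporting, since 12.3 requires the event to be related as well as unexpected.

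These points limit the size and direction. They do not answer the core: the definition of an SAE is fixed in the protocol, and it includes one route to the primary outcome.

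**Conclusion.** The point holds as a definitional defect of modest and uncertain effect. By the protocol's own list, a term live birth by planned caesarean is a success and an SAE at once, and the status of other birth admissions is left to each site. Crude SAE counts per randomised woman are therefore partly confounded with efficacy.

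On the text as written, the birth-related excess under PICSI is about 8–25 events. This rests on 24% v 29%, about 1,678 women per arm and an assumed 10–30% of births by elective caesarean. The overall SAE ratio could lie on either side of 1: about 0.80 to 1.15 with 15–50% of births logged, 10–50% of miscarriages admitted and miscarriage falling from 10% to 5%. An imbalance of unknown sign is still a poor basis for a safety judgement, because it reflects pregnancy outcomes rather than harm from the device.

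**What to change.** - **Section 12.2.1:** state that admission for birth, planned caesarean included, is not in itself an SAE, and that complications still qualify under 12.2. Take elective caesarean off the expected list.
- **Sections 12.2, 12.2.1 and 12.3:** reconcile them so that no ordinary birth admission meets the hospitalisation criterion in one section and counts as unexpected by omission in another.
- **SAE summaries by arm for the DMEC:** keep the count per randomised woman, and show pregnancy-outcome admissions (birth, miscarriage) separately from other SAEs. Do not rely on a per-clinical-pregnancy rate instead: it conditions on a post-randomisation event and, as step 5 shows, may leave the imbalance in place.

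The cost is a few lines of protocol wording and one extra split in the safety tables, with fewer SAE entries for sites. The small downside is that planned birth admissions no longer appear on the SAE log; the births remain recorded as pregnancy outcomes.

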## 12.3 Notification and Reporting of Serious Adverse Events

The National Research Ethics Service defines related and unexpected SAEs as follows:

- related' resulted from administration of any research procedure.
- 'unexpected' this type of event is not listed in the protocol as an expected occurrence

Only Serious Adverse Event (SAEs) that are considered to be 'related' and 'unexpected' are to be reported to the sponsor and PCTU QA manager within 24 hours of learning of the event and to the Main REC within 15 days in line with the required timeframe.

## 12.4 Urgent Safety Measures

The CI may take urgent safety measures to ensure the safety and protection of the clinical trial subjects from any immediate hazard to their health and safety, in accordance with Regulation 30. The measures should be taken immediately. In this instance, the approval of the Licensing Authority Approval prior to implementing these safety measures is not required. However, it is the responsibility of the CI to inform the sponsor and Main Research Ethics Committee (via telephone) of this event **immediately**.

The CI has an obligation to inform both the Main Ethics Committee **in writing within 3 days**, in the form of a substantial amendment. The sponsor and PCTU QA manager must be sent a copy of the correspondence with regards to this matter.

## 12.5 Annual Safety Reporting

The CI will send the Annual Progress Report to the main REC using the NRES template (the anniversary date is the date on the MREC "favourable opinion" letter from the MREC) and to the sponsor and PCTU QA manager.

### **13. STATISTICAL CONSIDERATIONS**

The analysis will be by intention to treat. Every attempt will be made to gather data on all women randomised, irrespective of compliance with the treatment protocol.

### 13.1 Trial Outcomes

#### 13.1.1 Primary outcome measures:

### 13.1.1.1 *Clinical*:

Live birth at ≥37 weeks' gestation following the first fresh ICSI treatment

### 13.1.1.2 Mechanism:

HBA score will be recorded on the day of PICSI / PVP-ICSI procedure and DGC washed sperm will be examined, retrospectively for disruption of chromatin architecture and DNA damage.

## 13.1.2 Secondary outcome measures:

### 13.1.2.1 Clinical:

- Clinical pregnancy rate based on detection of a fetal heartbeat or the presence of fetal sac at 6-9 weeks' gestation
- Miscarriage, defined as pregnancy loss after confirmation of clinical pregnancy
- Live birth <37 weeks' gestation

## 13.1.2.2 Mechanism:

Chromatin disruption in relation to DNA damage and DNA packaging anomalies in 45:90 interface samples and correlation between clinical and post-clinical HBA scores in relation to initial sperm concentration. The relationship between the tests of chromatin and DNA integrity with live birth outcome and miscarriage will be dynamically assessed by statistical modelling (please see section 13.7).

